## **Study Stopping Criteria**

### Comfort Assessment

The Comfort Assessment will be considered for stopping should 3 or more subjects experience any of the following:

- discontinue dosing due to persistent irritation deemed not to be due to underlying disease activity
- suffer persistent loss of 3 or more lines of visual acuity not explained by the condition under investigation and confirmed upon repeat testing
- develop persistent corneal opacities or severe keratitis
- suffer an IOP increase of 12 or more confirmed upon repeat testing
- subjects undergo sight threatening adverse events such as corneal melting or corneal ulceration

If the study is stopped for any of the above reasons, a lower dose may be considered for completion of the remainder of the study if deemed appropriate by the Sponsor and PI.

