	
by a rest day. Unless stopping criteria are implemented, subjects will proceed to receiving 4 consecutive days dosing of placebo or 0.1% TOP1630 TID (as described in Summary of Visit Schedule).
 
For the Safety and Efficacy Assessment, eligible subjects will be randomized to one of the treatments below (in the ratio of 1 active: 1 placebo) to be administered bilaterally TID for 28 days (from Visit 2b to Visit 4b).
 
1) TOP1630 Ophthalmic Solution 2) Placebo (Vehicle with no TOP1630)
 
TOP1630 dose selection will be based upon the evaluation of emergent (blinded) data from the Comfort Assessment and will not exceed the highest dose tested in that part of the study.
 
During a 7 day study run-in period prior to randomization, all subjects will receive Placebo Ophthalmic Solution (Vehicle) bilaterally at the same dosing frequency as TOP1630.

Summary of Visit Schedule:	
Comfort Assessment 8 visits over the course of 12 days Visit 1a = Day 1, 0.01% TOP1630 or Placebo TID; Comfort Assessment Visit 2a = Day 2, Physician Assessment Visit 3a = Day 3, 0.1 % TOP1630 or Placebo QD, Comfort Assessment Visit 4a = Day 4, Physician Assessment Visit 5a = Day 5, 0.1 % TOP1630 or Placebo TID; Comfort Assessment Visit 6a = Day 6, Physician Assessment Visit 7a = Day 8, 0.1% TOP1630 or Placebo TID, Comfort Assessment followed by dosing daily with 0.1% TOP1630 or Placebo TID at home for Day 9 , Day 10 and Day 11 Visit 8a = Day 12, Physician Assessment
 
Safety and Efficacy Assessment 4 visits over the course of approximately 5 weeks Visit 1b = Day <math>-7 \pm 1</math> day, CAE Screening Visit 2b = Day 1, CAE Confirmation / Baseline

	
Visit 3b = Day <math>15 \pm 1</math> day, 2-Week Follow-Up / CAE Test
 
Visit 4b = Day <math>29 \pm 2</math> days, 4-Week Follow-Up / CAE Test / Exit

Measures Taken to Reduce Bias:	This is a randomized treatment assignment, double masked study.
Study Population Characteristics	
Number of Subjects:	
Total 68
 
6 active and 2 placebo in the Comfort Assessment
 
30 active and 30 placebo in the Safety and Efficacy Assessment

Condition/Disease:	Dry Eye Syndrome

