Safety Measures:	
For the Comfort Assessment:
 

• Visual acuity (ETDRS)

• Slit-lamp biomicroscopy

• Adverse event query

• Vital Signs

• Drop Comfort Assessment

• Intraocular pressure (non-contact) at all Visits.

 
For the Safety and Efficacy Assessment:
 

• Visual acuity (ETDRS)

• Slit-lamp biomicroscopy

• Corneal Sensitivity

• Adverse event query

• Undilated Fundoscopy

• Vital Signs

• Drop Comfort Assessment

• Intraocular pressure (non-contact)

 
Stopping criteria will be utilized in the Comfort Assessment to ensure that an appropriate dose can be carried forward into the Safety and Efficacy Assessment. This may include use of a lower dose regimen in the multiple dose assessment of comfort. Stopping criteria will also be utilized during the conduct of the Safety and Efficacy Assessment.

Exploratory Efficacy Measures:	

• Corneal fluorescein staining using the Ora Calibra® Scale and NEI Scale

• Conjunctival lissamine green staining using the Ora Calibra® Scale and NEI Scale

• Visual Analogue Scale (VAS) for symptoms (Pre-CAE®)

• Tear film break-up time (TFBUT)

• Conjunctival redness the Ora Calibra® scale

• Schirmer Test at Visits 2b, 3b, and 4b

• Ora Calibra® Ocular Discomfort & 4-Symptom Questionnaire

• OSDI®

• Ora Calibra® Lid Margin Redness

• Ora Calibra® Posterior Lid Edge Evaluation

• OPI 2.0

• Ora Calibra® Ocular Discomfort Scale

Other:	Biomarker assessment by Impression Cytology (OPIA Eyeprim™)

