TOP1630 0.1% or Placebo TID	Comfort Assessment Morning 0.1% TOP1630 or Placebo Dose Slit Lamp Biomicroscopy, Comfort Assessment Afternoon 0.1 % TOP1630 or Placebo Dose Comfort Assessment Evening 0.1% TOP1630 or Placebo Dose Visual Acuity, Slit Lamp Biomicroscopy, IOP, and Comfort Assessment Subject leaves clinic at completion of Visit
Visit 6a (Day 6: 24 +/- 3 hrs after Day 5 dose): Physician Assessment	Medical/Medication Update, AE Query, Vital Signs Visual Acuity, Slit Lamp Biomicroscopy, IOP
Visit 7a (Day 8): Multi-Dose Phase Start	Medical/Medication Update, AE Query, Vital Signs Visual Acuity, Slit Lamp Biomicroscopy, IOP 0.1 % TOP1630 or Placebo TID (at home) Comfort Assessment (at home) Study Drug for at-home dosing and Comfort Questionnaire dispensed
Subject will dose 0.1% TOP1630 or Placebo TID at home on Days 8-11. No site visits.	
Visit 8a (Day 12: 24 +/- 3 hrs after first dose on Day 11): Study Exit	Collection of Study Drug/Comfort Questionnaire Medical/Medication Update, AE Query, Vital Signs Visual Acuity, Slit Lamp Biomicroscopy, IOP Urine Pregnancy Testing (as needed) Study Exit

Analysis of the Comfort Assessment will be conducted in a blinded manner to ensure study stopping criteria have not been met and to confirm the dose for the 4 week Safety and Efficacy Assessment. If study stopping criteria have been met, unmasking may be needed to fully assess the data prior to dose selection. A separate study plan will be created to outline the process for evaluation of stopping criteria and dose selection for the Safety and Efficacy Assessment.

For the Safety and Efficacy Assessment, 60 subjects at least 18 years of age with a subject-reported history of dry eye in both eyes and meeting all other study eligibility criteria will be randomized to receive treatment with TOP1630 Ophthalmic Solution (dose determined by outcome of Comfort Assessment) or placebo in a 1:1 ratio (approximately 30 subjects in each treatment group). This study will consist of two periods: a 7-day run-in period and a 28-day treatment period. A study flow chart appears below:

Visit 1b (Day -7 ± 1): Screening	Informed Consent Demographics, Medical/Medication & Ocular History Vital Signs Urine Pregnancy Testing (as needed) Symptom Questionnaires, Visual Acuity Pre-CAE® Eye Evaluations CAE® Exposure Post-CAE® Eye Evaluations
---	--

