## 9.2 Serious Adverse Events

An adverse event is considered serious if, in the view of either the investigator or sponsor, it results in any of the following outcomes:

- Death;
- A life-threatening adverse event;

Note: An adverse event is considered "life-threatening" if, in the view of either the investigator or sponsor, its occurrence places the patient or subject at immediate risk of death. It does not include an adverse event that, had it occurred in a more severe form, might have caused death.

- Inpatient hospitalization or prolongation of existing hospitalization;

Note: The term “inpatient hospitalization” refers to any inpatient admission (even if less than 24 hours). For chronic or long-term inpatients, inpatient admission includes transfer within the hospital to an acute/intensive care inpatient unit. Inpatient hospitalization does not include: emergency room visits; outpatient/same-day/ambulatory procedures; observation/short stay units; rehabilitation facilities; hospice facilities; nursing homes; or clinical research/phase 1 units.

Note: The term “prolongation of existing hospitalization” refers to any extension of an inpatient hospitalization beyond the stay anticipated or required for the reason for the initial admission as determined by the investigator or treating physician.

- A persistent or significant incapacity or substantial disruption of the ability to conduct normal life functions;

Note: A serious adverse event specifically related to visual threat would be interpreted as any potential impairment or damage to the subject’s eyes (e.g., hemorrhage, retinal detachment, central corneal ulcer or damage to the optic nerve).

- A congenital anomaly/birth defect.

Important medical events that may not result in death, are not life-threatening, or require hospitalization may be considered serious when, based upon appropriate medical judgment, they may jeopardize the patient or subject and may require medical or surgical intervention to prevent one of the outcomes listed in this definition.

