#### **9.4 Procedures for Unmasking of Study Drug**

All subjects, investigators, and study personnel involved with the conduct of the study will be masked with regard to treatment assignments. When medically necessary, the investigator may need to determine what treatment arm has been assigned to a subject. When possible (i.e., in non-emergency situations), Ora and/or the study

sponsor should be notified before unmasking study drug. Subjects will also be unmasked for treatment-related SAEs or pregnancies in a similar manner. The Investigator should complete the appropriate forms (per the Safety Plan) and, when possible, discuss with Ora, the Medical Monitor, and TopiVert Pharma, Ltd whether unmasking is required. The Investigator can unmask study drug assigned to a subject using the black blinding laminate label that was placed in the Source Document from the subject's study drug kit by removing the protective plastic over it and then scratching it off. Documentation must be completed by the unmasking Investigator and filed in the subject's study file. The subject's study file must include documentation for the unmasking reason and date along with the signature and name of the person who unmasked the subject. A copy of the appropriate forms must be provided to Ora for the Trial Master File. Unmasked subjects will be discontinued from the study.

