#### 10.4.8 Interim Analyses

No interim analyses are planned; however, assessments from the Comfort Assessment will be analyzed in a blinded manner to ensure study stopping criteria have not been met and to confirm the dose for the 4 week Safety and Efficacy Assessment. If study stopping criteria have been met, unblinding may be needed to fully assess the data prior to dose selection.

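### The only numeric group rule before the 28-day dose is chosen needs 3 of 8 subjects for every event type, with no lower count for sight-threatening events

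*Protocol*

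**What the plan says.** **The rule.** Protocol Section 5.3, Study Stopping Criteria, Comfort Assessment: "The Comfort Assessment will be considered for stopping should 3 or more subjects experience any of the following". Five items follow: stopping dosing for persistent irritation, persistent loss of 3 or more lines of acuity, persistent corneal opacity or severe keratitis, a confirmed IOP rise of 12 or more, and finally "subjects undergo sight threatening adverse events such as corneal melting or corneal ulceration". No item has its own count. The Synopsis gives 6 active and 2 placebo subjects, and the rule does not separate the arms.

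**Its link to the dose.** The Synopsis (Safety Measures) says the Comfort stopping criteria are used "to ensure that an appropriate dose can be carried forward into the Safety and Efficacy Assessment". Section 4 says the masked analysis of the Comfort data is done "to ensure study stopping criteria have not been met and to confirm the dose for the 4 week Safety and Efficacy Assessment". Section 10.4.8 repeats that "assessments from the Comfort Assessment will be analyzed in a blinded manner to ensure study stopping criteria have not been met". The Synopsis (Dosage/Dose Regimen) bases the dose on evaluation of the emerging blinded data and adds that it "will not exceed the highest dose tested in that part of the study". Section 4 leaves the process to a separate study plan, which is not among the documents supplied.

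**How single events are treated elsewhere.** Section 9.2 gives as examples of a visual-threat SAE "hemorrhage, retinal detachment, central corneal ulcer or damage to the optic nerve". Section 9.3.2 requires every SAE to be reported within 24 hours. Section 9.4 says: "Subjects will also be unmasked for treatment-related SAEs or pregnancies in a similar manner". The withdrawal criteria in 5.3 let any one subject be discontinued for a sight-threatening event.

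**The concern.** A count of 3 is a sensible filter for irritation, which is common in dry eye and hard to attribute in one subject. It is a poor filter for corneal melting or ulceration, where a single case in 8 subjects should make a sponsor stop and look. The protocol takes that view of the individual in Sections 5.3, 9.2 and 9.4, but its group rule weighs a melting cornea the same as a subject who gives up drops because they sting.

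Section 1 states that this is the first study in man. The 8 Comfort subjects are therefore the only human data before about 30 subjects take the chosen dose three times a day for 28 days. If the one numeric rule at this step is unlikely to respond to a high rate of severe ocular events, the protection of those subjects rests on judgement for which the protocol states no minimum.

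**Working it through.** **The plan's own figure.** The documents give no probability for the 3-subject rule. The only probability stated is in Section 10.3: 79% for detecting an AE with a 5% rate in the 28-day part. It reproduces per arm: 1 − 0.95^30 = 0.785. With n = 60 it would be 0.954. The same exact binomial calculation is used below.

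**Inputs.** From the documents: 6 active and 2 placebo subjects; threshold 3, arms pooled. Assumed, because the documents give no rate: p, the chance that an active subject has at least one severe ocular event (sight-threatening event, persistent opacity or severe keratitis, or persistent unexplained loss of 3 or more lines) during the Comfort Assessment. The base case has no other listed event and none on placebo. The item list is read as any combination across subjects; if 3 subjects had to share the same item, the rule would be harder to reach.

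**Headline case.** Two of 6 active subjects affected and nobody else: 2 < 3, so the rule is unmet. The observed rate is 2/6 = 33%, exact 95% CI 4.3% to 77.7%.

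**Chance of reaching each threshold.** With X ~ Binomial(6, p):

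- 3 or more: 1 − [(1−p)^6 + 6p(1−p)^5 + 15p²(1−p)^4]
- 1 or more: 1 − (1−p)^6

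At p = 0.20 the first is 1 − (0.2621 + 0.3932 + 0.2458) = 0.0989, and the second is 1 − 0.2621 = 0.7379.

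| Assumed p | 3 or more (current) | 2 or more | 1 or more |
|---|---|---|---|
| 5% | 0.2% | 3.3% | 26% |
| 10% | 1.6% | 11.4% | 47% |
| 20% | 9.9% | 34.5% | 74% |
| 30% | 25.6% | 58.0% | 88% |

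The current rule has an even chance of being reached only at p = 42%, and an 80% chance at p = 59%. A one-subject trigger has an 80% chance at p = 24%.

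**Sensitivity to the base case.**

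- Placebo events: with a 10% rate of any listed event in the 2 placebo subjects, P(total ≥ 3) = P(X≥3) + P(X=2) × 0.19 + P(X=1) × 0.01. At p = 20% this is 0.0989 + 0.2457 × 0.19 + 0.3932 × 0.01 = 15%; at p = 30% it is 32%.
- Other listed events in active subjects: if a different listed event occurs in other active subjects at the same rate again, the any-event rate is 40% or 60%, and the current rule is reached in 46% or 82% of trials.

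**False alarms under a one-subject trigger.** At an assumed background rate of 0.1% to 1% per subject, across 8 subjects: 1 − 0.999^8 = 0.8% and 1 − 0.99^8 = 7.7%.

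**The case against.** The strongest reply is that the 3-subject count is not what stands between two corneal ulcers and the 28-day dose.

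A reader might infer that it is the only check on that dose. The documents do not support this. Dose choice rests on evaluation of all emerging blinded data. Section 4 assigns the process to a separate plan that may be stricter. Visual acuity, slit lamp and IOP are examined at the physician visits on Days 2, 4, 6 and 12. A corneal ulcer meeting 9.2 goes to the medical monitor and sponsor within 24 hours; if it is treatment-related, the subject is unmasked and, under 9.4, discontinued. Section 8.7 allows the study to be stopped at any time, and the 28-day part has its own rule (more than 10 discontinuations).

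A reader might also infer that unmet criteria mean 0.1% passes automatically. No sentence says so. The review has two purposes, checking the criteria and confirming the dose, and even a met rule leads only to stopping being considered.

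The base-case probabilities also flatter the complaint. A drug that ulcerates corneas would plausibly cause other listed events, and the rule pools them.

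All of this stands, and two ulcers would not go unseen. What it does not supply is a required action. The individual criteria and 9.4 deal with the affected subject, not the others. SAE reporting informs people but prescribes no pause. The 28-day rule acts after the dose is chosen. Section 4 ties unmasking for dose selection to the stopping criteria being met. The unseen plan may close the gap, but the protocol sets no minimum for it.

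**Conclusion.** The point holds as a gap in the written group rule, not as a claim that the dose is unguarded. The only numeric group-level criterion applying before dose selection treats sight-threatening events no more strictly than irritation, and 2 of 6 active subjects with such events can leave it unmet.

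The size depends on assumed rates. Across 5% to 30% with no other listed events, the current rule is reached in 0.2% to 25.6% of trials and a one-subject trigger in 26% to 88%. With many other listed events in active subjects, the current rule's performance improves substantially, so its base-case figures are near the low end. The headline case needs no assumed rate.

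This is a cheap improvement to subject protection in a first study in man. It does not show that the sponsor would have carried an unsafe dose forward.

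**What to change.** In Section 5.3 (Comfort Assessment), keep the 3-subject count for irritation and IOP, and add:

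*One or more subjects with a sight-threatening event, persistent corneal opacity or severe keratitis, or confirmed persistent unexplained loss of 3 or more lines will pause further dosing at that concentration and dose confirmation, pending a documented review by the medical monitor, sponsor and PI (unmasked if needed), which decides whether to continue, lower the dose or stop.*

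Cross-refer to it from the dose-selection text in the Synopsis and Section 4, and from the separate plan.

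Dose reduction should not be automatic. Only two strengths exist, so a forced step down from 0.1% is tenfold. The relationship category None in 9.1.2 is defined so strictly that an uncertain background event would probably be rated Possible or Unclassified. At a 1% background rate, the chance of at least one such event among the 6 active subjects is 1 − 0.99^6 = 5.9%. That is too high a price for a mandatory step, but acceptable for a review.

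**Cost.** One sentence and cross-references, with no extra subjects, procedures or supply. A false alarm costs a review, a short delay and possibly the unmasking of one subject, who would then be discontinued under 9.4. Because the Comfort visits fall on fixed days, the text should say that visits moved by a pause are not deviations. There are no site visits between Days 8 and 12, so an event in the home-dosing period that the subject does not report would be found only on Day 12; the pause would then act on dose confirmation.

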### Safety and Efficacy Assessment

The Safety and Efficacy Assessment will be considered for stopping should more than 10 subjects discontinue dosing due to any of the following:

- persistent irritation deemed not to be due to underlying disease activity
- persistent loss of 3 or more lines of visual acuity not explained by the condition under investigation and confirmed upon repeat testing
- persistent corneal opacities or severe keratitis
- an IOP increase of 12 or more confirmed upon repeat testing

- other sight threatening adverse events such as corneal melting or corneal ulceration

## 6 STUDY PARAMETERS

### 6.1 Safety Measures

- Visual acuity (ETDRS)
- Slit-lamp biomicroscopy
- Corneal sensitivity (Pre-CAE®)
- Adverse event query
- Undilated fundoscopy
- Vital signs at all visits
- Drop comfort assessment
- Intraocular pressure (non-contact)

### 6.2 Exploratory Efficacy Measures

- Corneal fluorescein staining on the Ora Calibra® and NEI scales
- Conjunctival lissamine green staining on the Ora Calibra® and NEI scales
- Visual Analogue Scale (VAS) (Pre-CAE®)
- Tear film break-up time
- Conjunctival redness the Ora Calibra® scale
- Schirmer Test at Visits 2b, 3b, and 4b
- Ora Calibra® Ocular Discomfort & 4-Symptom Questionnaire
- OSDI®
- Ora Calibra® Lid Margin Redness
- Ora Calibra® Posterior Lid Edge Evaluation
- OPI 2.0
- Ora Calibra® Ocular Discomfort Scale

### 6.3 Biomarkers

- Impression Cytology (OPIA EyeprimTM).

## 7 STUDY MATERIALS

### 7.1 Study Drug(s)

#### 7.1.1 Formulations

Comfort Assessment

- 0.01% TOP1630 Ophthalmic Solution

- 0.1% TOP1630 Ophthalmic Solution
- Placebo Ophthalmic Solution (Vehicle with no TOP1630)

Run-In

- Placebo Ophthalmic Solution (Vehicle with no TOP1630)

Safety and Efficacy Assessment

- TOP1630 Ophthalmic Solution (dose determined by outcome of Comfort Assessment)
- Placebo Ophthalmic Solution (Vehicle with no TOP1630)

7.1.2 Dispensation Schedule

Comfort Assessment

- At Visit 1a, qualified subjects will be randomized and receive their assigned study drug Comfort Kit. They will administer the first three doses of placebo or 0.01% TOP1630 in office.
- At Visit 3a, subjects will administer a single dose of placebo or 0.1% TOP1630 from their assigned study drug Comfort Kit. Unless stopping criteria (as outlined in Section 5.3) are met, the remaining doses for each subject for the remainder of the Comfort Assessment will be at the 0.1% concentration of TOP1630 or placebo. If stopping criteria are met after the introduction of the 0.1% TOP1630, the Comfort Assessment study may proceed with the subjects' dosing with the lower concentration 0.01% TOP1630 (or placebo).
- At Visit 5a, subjects will dose TID in office with placebo or 0.1% TOP1630 from their assigned study drug Comfort Kit.
- At Visit 7a, a Take Home Kit from their assigned study drug Comfort Kit will be dispensed to subjects for at-home dosing TID with placebo or 0.1% TOP1630 from days 8 through 11 (4 days TID).
- At Visit 8a all study drug will be collected.

Safety and Efficacy Assessment

- At the end of Visit 1b, qualified subjects will receive a kit of run-in (Placebo) for one week, dosing TID until Visit 2b. Subject will be instructed to dose in 6-hour intervals in the morning, afternoon, and in the evening before bed.
- The run-in kit will be collected at the beginning of Visit 2b and accountability will be performed by a study technician.
- At the end of Visit 2b, qualified subjects will be randomized and the first dose of study drug will be administered in office, and subjects will take remaining doses at home.

- At the end of Visit 2b, subjects will be given two kits of 24 bottles each of TOP1630 Ophthalmic Solution or placebo for TID dosing.
- At Visit 3b, subjects will receive two new kits of the same test article they were previously randomized to (at Visit 2b) for TID dosing.
- At Visits 3b and 4b, remaining/unused study drug will be collected from subjects for drug accountability.
- Subjects will be instructed to not use run-in (at Visit 2b) or study drug on the day of visits (Visit 3b and 4b) prior to the visit.

